Appendix 6: Safety Plan: Management of Identified and Potential Risks

There were no events of neutropenia or leukopenia in adult patients with ASD taking 10 mg in Study BP30153.

Please refer to the Balovaptan Investigator's Brochure for further details.

Overall, the available clinical safety database does not suggest a causal neutropenia risk due to balovaptan administration. However, participants receiving concomitant treatment with clozapine will be excluded due to relatively high risk of agranulocytosis. Patients with clinically significant hematologic abnormalities or history of blood dyscrasias, hematologic malignancies, or myelosuppression (including iatrogenic) will be excluded from the study. Safety surveillance in Study BN43546 includes hematological monitoring and check for clinical signs and symptoms of infection.

A6–1.3 POTENTIAL RISK OF SKELETAL MUSCLE TOXICITY

Skeletal muscle degeneration associated with increases in creatine phosphokinase (CPK) was noted after treatment with a high dose of balovaptan in male rats. After treatment completion, these effects promptly reversed. The mechanism of balovaptan effects on skeletal muscle in rats is unclear. In vitro experiments indicate that M3 may play a major role. This is consistent with this finding only being observed in male rats that have higher M3 exposures than female rats. No mitochondrial toxicity or cytotoxicity due to cell-cycle inhibition was demonstrated. Based on AUC values measured at NOAEL, the margins relative to anticipated AUC after 10 mg QD balovaptan in adult humans are approximately 8-fold with regard to parent and approximately 10-fold with regard to M3.

In the literature, the involvement of the V1a receptor to regain muscle integrity after tumor necrosis factor- α exposure has been suggested based on V1a receptor gene delivery experiments in mice (Costa et al. 2014). No skeletal muscle effects of balovaptan have been observed in dogs.

In humans, a severe adverse event of rhabdomyolysis was reported in a patient with ASD treated with 1.5 mg QD balovaptan, and occasional CPK elevations were noted in clinical trials. Nevertheless, the totality of clinical data available to date (including analysis of CPK values and musculoskeletal adverse events) does not indicate a safety alert for skeletal muscle toxicity due to balovaptan. This conclusion is based on the observations that CPK elevations were also measured in placebo-treated subjects with ASD and that treatment-emergent CPK elevations decreased when treatment was continued. CPK levels will be monitored during the study drug treatment period and with a defined CPK-related adverse event of special interest.

Please refer to the Balovaptan Investigator's Brochure for additional details.

Appendix 6: Safety Plan: Management of Identified and Potential Risks

Overall, the risk of skeletal muscle toxicity for this study is considered minimal given the safety margin relative to NOAEL noted in rats, the absence of skeletal muscle toxicity in dogs, and the clinical trial experience not indicating skeletal muscle toxicity.

In addition to adverse event monitoring, CPK levels will be used to monitor for possible occurrences of skeletal muscle toxicity.

A6–1.4 POTENTIAL RISK OF CARDIAC TOXICITY

In rats dosed from post-natal day (PND) 14 (juvenile to adult), an increase in heart weight was observed at the highest dose tested. The increase in heart weight was considered non-adverse based on the lack of associated creatine phosphokinase (CPK) changes or a histopathological correlate. In the 26-week Good Laboratory Practice (GLP) toxicology study in adult rats, an increased incidence of spontaneous cardiomyopathy changes was observed, but these changes were considered to be non-adverse exacerbations due to stress. Cardiac pathologies were not observed when balovaptan was administered to dogs in GLP toxicology studies.

Intense exploration of interference with cardiac ion channels for balovaptan and its M3 and M2, did not reveal a pre-clinical safety alert for QTc prolongation.

In clinical trials, treatment with balovaptan (10 mg QD) for more than 12 weeks did not produce a cardiac toxicity alert based on clinical adverse event reporting and monitoring with cardiac biomarkers (troponin and N-terminal prohormone of brain natriuretic peptide [NT-proBNP]). Results from a thorough QT study are available (Study WP40734) and confirmed absence of corrected QT interval (QTc) prolonging effects after administration of balovaptan at 10 mg and 50 mg QD dosing regimens.

The risk of cardiac toxicity in Study BN43546 is considered minimal because of the lack of cardiac toxicity in dogs, the delayed onset of cardiac effects in rats (which were considered stress-related rather than direct cardiac effects, and in particular the absence of a safety alert from dedicated cardiac monitoring in clinical trials.

Safety monitoring in Study BN43546 will include *ECG*, adverse event monitoring and assessment of high-sensitivity cardiac troponin T (hs-cTnT) in conjunction with a follow-up plan if elevated hs-cTnT levels are measured.

A6–1.5 POTENTIAL RISK OF PERIPHERAL NEUROPATHY

In the 26-week toxicity study in rats and in two subsequent supplementary 26-week toxicology studies in adult and juvenile rats, test article–related microscopic effects were observed in multiple peripheral nerves (degeneration of the perineurium with edema and cellular infiltrates). The onset of peripheral nerve histopathology effects was seen as early as 13 weeks of treatment, and further progression noted after 26 weeks of

The risk of study treatment linked peripheral neuropathy for participants in this study is considered to be minimal because of the safety margins relative to the NOAEL in rats, no neurohistopathologies have been noted in dogs, and the results from neurological monitoring in clinical trials have not generated a signal for balovaptan caused peripheral neuropathy.

This study excludes participants with signs and symptoms of peripheral neuropathy. Neurologic examinations focusing on the lower limbs (longer nerves being more susceptible to neuropathy) will be completed during the study (see the schedule of

Appendix 6: Safety Plan: Management of Identified and Potential Risks

activities in Section 1.3, Table 1). The neurological examination must be conducted as outlined in Appendix 7.

Please refer to the Balovaptan Investigator's Brochure for additional details.

A6–1.6 POTENTIAL RISK OF BLEEDING

Theoretically, due to expression of V1a receptors on platelets, antagonism could impact platelet aggregation. Neither animal studies nor clinical studies of balovaptan up to 50 mg for 2 weeks have shown a bleeding risk.

Selective serotonin reuptake inhibitors (SSRIs) have been shown to possess a bleeding risk, even though fairly small (Dalton et al. 2006; Serebruany 2006). In the ASD clinical trials 156 subjects were receiving concomitant SSRI medications. No bleeding risk events were reported.

Patients with a history of coagulopathies or other bleeding disorders or current clinically relevant bleeding event will be excluded from the study.

Treatment with study drug should be stopped about 1 week prior to surgeries and invasive procedures anticipated to be associated with major blood losses or bleedings in sensitive organs (e.g., eye, brain, and spinal cord).

A6–1.7 POTENTIAL RISK OF BLOOD PRESSURE CHANGES

Given the vasoconstrictive effects on systemic resistance blood vessels of vasopressin mediated through the V1a receptor, blockade of this receptor by balovaptan may lead to reductions in blood pressure. However, in a cardiovascular safety pharmacology study conducted in telemetered dogs, an increase in blood pressure was observed with an approximately 19-fold margin between the NOAEL C_{max} for the dog (1917 ng/mL) and the predicted highest average C_{max} for participants in Study BN43546 (103 ng/mL). The physiology behind the blood pressure increase seen in dogs is unknown.

Ambulatory blood pressure monitoring of healthy volunteers was included in clinical Study WP40734 (a thorough QT study), which evaluated both a 10 mg QD and a 50 mg QD treatment regimen over 2 weeks. No significant blood pressure changes emerged; in particular, no decrease in blood pressure measurements was observed.

The absence of a decrease in blood pressure may be explained by blood concentrations of vasopressin being too low to meaningfully activate the V1a receptor and/or by the multifactorial blood pressure regulation system in the sense that blockade of the V1a receptor is compensated by alternative regulator pathways.

Appendix 6: Safety Plan: Management of Identified and Potential Risks

Nevertheless, participants should be instructed to avoid rapid movements when moving from supine to sitting to standing position. Blood pressure will be monitored at regular intervals during the treatment period.

A6–2 MANAGEMENT OF PARTICIPANTS WHO EXPERIENCE ADVERSE EVENTS

A6–2.1 DOSE MODIFICATIONS

No dose modifications will be allowed in this study.

A6–2.2 TREATMENT INTERRUPTION

Balovaptan may be withheld in participants who experience toxicity considered to be related to study drug. If balovaptan *has been* withheld for >10 days because of toxicity, the participant should be discontinued from study drug, unless resumption of treatment is approved *by the* investigator *following consultation* with the Medical Monitor. Balovaptan may be withheld for reasons other than toxicity (e.g., surgical procedures) *at the investigator's discretion following consultation* with *the* Medical Monitor. The investigator *may consult* the Medical Monitor *to* determine the acceptable length of treatment interruption.

A6–2.3 MANAGEMENT OF SEIZURES

While the risk of seizure/convulsive events due to balovaptan is considered minimal, local treatment guidelines should be followed to manage such events should they occur.

Participants experiencing an adverse event of convulsion should be seen by the relevant physician immediately and as soon as possible, they should be referred to a clinical expert in the area of epilepsy to define diagnostic steps. These may include 24-hour dedicated video EEG monitoring. Collection of blood and urine samples is recommended to measure, as applicable, levels of balovaptan, any anti-epileptic drugs, drugs of abuse, glucose, and electrolytes (sodium, potassium, chloride, magnesium). If possible, a blood sample for prolactin should be taken within 1 hour since seizure onset. Psychogenic non-epileptic seizures are reported to occur in patients with PTSD (Popkirov et al. 2019; Perez et al. 2016). Vital signs should be monitored and a 12-lead ECG recorded as soon as possible.

Depending on the nature and severity of the convulsive event, it may not result in permanent study treatment discontinuation.

Adverse events of seizure/convulsion should be discussed with the Medical Monitor as soon as possible.

A6–2.4 MANAGEMENT OF NEUTROPENIA

As outlined above, the risk of relevant neutropenia due to balovaptan is considered low.

In case of emergent neutropenia, treatment discontinuation is suggested for participants who meet the following criterion for decreased ANC:

- If the ANC falls $<800/\mu\text{L}$ and the low ANC is confirmed in a second sample to be obtained within about 3 days, the investigator should consider treatment discontinuation. In cases of ANC-related treatment discontinuation, additional laboratory parameters should be considered by the investigator, including fibrinogen, high-sensitivity C-reactive protein (hs-CRP), and an assessment for anti-neutrophil cytoplasmic antibody (ANCA).
- Follow-up management of participants who experience fever and/or infection in the context of reduced ANC should be discussed with the Medical Monitor and the participant may be referred to a specialist to decide on next steps.

ANC values below $800/\mu\text{L}$ (confirmed), should be reported as an adverse event of special interest (see [Appendix 3](#), Section [A3–5](#)).

A6–2.5 MANAGEMENT OF BLEEDING

While the risk of bleeding events due to balovaptan is considered low, should such an event occur, a review of concomitant medications should be undertaken especially those that have known bleeding risks. Based on the clinical significance of the bleeding, treatment with study drug should be interrupted and may be permanently discontinued if no alternative causative factors of the bleeding adverse event can be identified and removed.

Blood samples to assess coagulation parameters (INR, PT, aPTT) as well as balovaptan blood levels should be taken.

A6–2.6 MANAGEMENT OF SKELETAL MUSCLE TOXICITY

Elevated CPK levels at screening and baseline are not exclusions as long as serum creatinine and potassium values do not exceed the upper limit of normal (ULN). In instances where CPK is increased more than $2\times\text{ULN}$ at screening, additional CPK, creatinine, and potassium samples should also be obtained at Week 2 of treatment. Samples from screening, baseline, Week 2, and Week 6 can then indicate whether an elevated CPK level observed at screening is part of a fluctuation because of physical exercise, for example, or is indicative of inherently elevated CPK levels in an individual participants. Participants are advised to abstain from intense physical exercise and to report musculoskeletal adverse events to the Investigator promptly.

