- ^t Includes evaluation of the head, eyes, ears, nose, and throat, and the cardiovascular, dermatologic, musculoskeletal, respiratory, gastrointestinal, and neurologic systems. Complete physical examinations will not include pelvic, rectal, or breast examinations. Record abnormalities observed at screening on the General Medical History and Baseline Conditions eCRF. At subsequent visits, record new or worsened clinically significant abnormalities on the Adverse Event eCRF. Limited, symptom-directed physical examinations should be performed as clinically indicated. Changes from baseline abnormalities should be recorded in patient notes. New or worsened clinically significant abnormalities should be recorded as adverse events on the Adverse Event eCRF.

Table 1 Schedule of Activities (cont.)

- ^u Site personnel will check for any emergence of clinical signs and symptoms of infection according to semi-structured questionnaire ([Appendix 9](#)). This will occur either by telephone call or in person *site* visits at Weeks 4, 6, 9, and 12.
- ^v Twelve-lead ECGs are to be performed after the participant has been in a supine position for 5 minutes. ECGs for each participant should be obtained from the same machine whenever possible and performed prior to any blood draws. ECGs obtained at baseline will be in triplicate. All others will be single recordings. In the event of prolongation of the QTc interval, an unscheduled PK sample should be obtained.
- ^w Hematology includes WBC count, RBC count, hemoglobin, hematocrit, platelet count, and differential count (neutrophils, eosinophils, basophils, monocytes, lymphocytes, and other cells).
- ^x Serum chemistry includes sodium, potassium, chloride, bicarbonate, glucose, BUN or urea, creatinine, CPK, total protein, albumin, phosphorus, calcium, total and direct bilirubin, ALP, ALT, AST, uric acid, LDH, cholesterol, LDL cholesterol, HDL cholesterol, triglycerides, including hs-cTnT. If CPK value exceeds 2×ULN at baseline, CPK, creatinine, and potassium levels should be monitored at Week 2.
- ^y The C-SSRS Baseline/Screening version should be used at the first screening visit; subsequent visits should use the C-SSRS Since Last Visit version.
- ^z Wearable device to be distributed and data collected 7 days prior to randomization (Day 1).

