8.3.7 Adverse Events of Special Interest

Adverse events of special interest are required to be reported by the investigator to the Sponsor immediately (i.e., no more than 24 hours after the investigator becomes aware of the event; see Section [A3–5](#) for reporting instructions). Adverse events of special interest for this study are as follows:

- Cases of potential drug-induced liver injury that include an elevated ALT or AST in combination with either an elevated bilirubin or clinical jaundice, as defined by Hy's Law (see Section [A3–7.6](#))
- Suspected transmission of an infectious agent by a study treatment, as defined below:

Any organism, virus, or infectious particle (e.g., prion protein transmitting transmissible spongiform encephalopathy), pathogenic or non-pathogenic, is considered an infectious agent. A transmission of an infectious agent may be suspected from clinical symptoms or laboratory findings that indicate an infection in a participant exposed to a medicinal product. This term applies only when a contamination of the study treatment is suspected.

- ANC values $<800/\mu\text{L}$ and confirmed in a second sample.
- Creatine phosphokinase (CPK) values triggering a change in monitoring schedule and also when:
 - CPK values exceed $10\times\text{ULN}$ for several days without trend of normalization according to CPK half-life in plasma
 - CPK increases associated with a relevant decrease in kidney function and no alternative explanation exists
 - CPK values increase again to similar values as noted before when treatment has been re-started.

- Cases of neurological abnormalities emerging from adverse event reporting or neurological examination (see Section 8.2.3) that are potentially indicative of dysfunction of peripheral nerves or otherwise represent a neurological deficit and for which no other explanation is apparent (see Safety Plan: Management of Identified and Potential Risks in Appendix 6, Section A6–2.9 for further details on when a measurement of the nerve conduction velocity (NCV) may be needed).

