Appendix 2: Clinical Safety Laboratory Tests

Table A2-1 Protocol-Required Safety Laboratory Assessments

Central Laboratory Tests

• Hematology: WBC count, RBC count, hemoglobin, hematocrit, platelet count, and differential count (neutrophils, eosinophils, basophils, monocytes, lymphocytes, and other cells)• Chemistry panel (serum): bicarbonate, sodium, potassium, chloride, glucose, BUN or urea, creatinine, CPK, total protein, albumin, phosphorus, calcium, total and direct bilirubin, ALP, ALT, AST, uric acid, and LDH If CPK value exceeds 2× ULN at baseline, creatinine and potassium levels should be monitored at Week 2• Lipids: total cholesterol, LDL cholesterol, HDL cholesterol, and triglycerides• Cardiac biomarkers: hs-cTnT (troponin T)• Coagulation: INR, aPTT, and PT• HIV serology: HIV-1 antibody, HIV-1/2 antibody, and HIV-2 antibody• HBV serology: HBsAg and total HBcAb for all individuals; HBV DNA for individuals with negative HBsAg tests and a positive total HBcAb test• HCV serology: HCV antibody for all individuals• Lipids: cholesterol, LDL cholesterol, HDL cholesterol, and triglycerides• Quantitative immunoglobulins: IgA, IgG, IgM, and IgE• Pregnancy test All women of childbearing potential will have a serum pregnancy test at screening. Urine pregnancy tests will be performed at specified subsequent visits. If a urine pregnancy test is positive, it must be confirmed by a serum pregnancy test.• Urinalysis, including dipstick (pH, specific gravity, glucose, protein, ketones, and blood). Microscopic examination performed at the central laboratory if blood and/or protein results are positive or strongly positive. If there is an explanation for the positive dipstick results (e.g., menses), it should be recorded and there is no need to perform microscopy and culture.

HBcAb=hepatitis B core antibody; HBsAg=hepatitis B surface antigen; HBV=hepatitis B virus; HCV=hepatitis C virus; HDL=high-density lipoprotein; hs-cTnT=high-sensitivity cardiac troponin T; LDL=low-density lipoprotein.

Investigators must document their review of each laboratory safety report.

Appendix 3

Adverse Events: Definitions and Procedures for Recording, Evaluating, Follow-Up, and Reporting

TABLE OF CONTENTS

A3-1	Definition of Adverse Event.....	90
A3-2	Definition of Serious Adverse Event	91
A3-3	Recording and Follow-Up of Adverse Events and/or Serious Adverse Events	92
A3-3.1	Adverse Event and Serious Adverse Event Recording.....	92

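### The extra Week 2 CPK check is triggered by the baseline value in two places and by the screening value in a third, and one of the three omits the repeat CPK

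*Combined protocol and SAP*

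**What the plan says.** The extra Week 2 check appears in three places, all in current text and all with the same 2×ULN threshold.

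- Section 1.3, Table 1, footnote x: "If CPK value exceeds 2×ULN at baseline, CPK, creatinine, and potassium levels should be monitored at Week 2".
- Appendix 2, Table A2-1, under the chemistry panel: "If CPK value exceeds 2× ULN at baseline, creatinine and potassium levels should be monitored at Week 2".
- Appendix 6, Section A6-2.6: when CPK is above 2×ULN at screening, "additional CPK, creatinine, and potassium samples should also be obtained at Week 2 of treatment".

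A6-2.6 also gives the purpose of the extra sample: "Samples from screening, baseline, Week 2, and Week 6 can then indicate whether an elevated CPK level observed at screening" is a passing fluctuation or a stable feature of that person.

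Table 1 schedules full serum chemistry, which includes CPK, at screening, Week 0, Week 6, Week 12, the Week 14 safety follow-up and early discontinuation. Section 9.4.1 defines baseline as the latest assessment no later than the day of first dosing, which is normally the Day 1 sample.

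**The concern.** The passages disagree on two things: which visit's value triggers the check, and whether CPK itself is measured again. The first decides who has the extra sample. The second decides whether that sample can serve its stated purpose.

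The people concerned can be in the study. A6-2.6 does not exclude raised CPK at screening or baseline, provided that creatinine and potassium are not above ULN. Skeletal muscle toxicity is one of the potential risks in the safety plan. Section A6-1.3 records a severe rhabdomyolysis event in an earlier study at 1.5 mg QD, although it rates the risk in this study as minimal. With about 12 sites (Appendix A1-5), staff who work from different pages could apply different rules. With about 15 participants per arm (Section 9.2), a difference of one or two people in who has early CPK data would be visible in a by-arm laboratory summary.

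**Working it through.** The plan states no figure to reproduce here. The check is a comparison of the texts, plus one interval.

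**Step 1. The three rules side by side.**

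| Place | Trigger (CPK >2×ULN) | Week 2 tests |
|---|---|---|
| Table 1, footnote x | Baseline | CPK, creatinine, potassium |
| Table A2-1 | Baseline | Creatinine, potassium |
| A6-2.6 | Screening | CPK, creatinine, potassium |

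The difference in tests does not follow the difference in trigger. Footnote x and A6-2.6 agree on the tests and differ on the visit. Footnote x and Table A2-1 agree on the visit and differ on the tests.

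**Step 2. Are screening and baseline the same sample?** No. Table 1 schedules chemistry at both visits, A6-2.6 names them as separate members of a four-sample series, and the Section 9.4.1 definition points to Day 1 when a Day 1 sample exists. The two words cannot be read as synonyms.

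**Step 3. Apply each rule to the four possible cases.**

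| CPK >2×ULN at | Footnote x | Table A2-1 | A6-2.6 |
|---|---|---|---|
| Both visits | Three tests | Two tests, no CPK | Three tests |
| Screening only | None | None | Three tests |
| Baseline only | Three tests | Two tests, no CPK | None |
| Neither visit | None | None | None |

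The passages disagree on who is sampled in two cases (screening only, baseline only). They disagree on whether CPK is repeated in the two cases where Table A2-1 applies (both visits, baseline only). Only the last case has no disagreement.

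**Step 4. Is the series in A6-2.6 complete under each rule?** It needs screening, baseline, Week 2 and Week 6 CPK. Under Table A2-1 taken literally, the Week 2 value is missing even for someone high at both earlier visits.

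**Step 5. Is there a scheduled substitute?** No routine CPK falls between Day 1 and Week 6 (Day 42). The nominal gap is 42 − 1 = 41 days. With the ±3-day window at Week 6 it is 38 to 44 days. An early discontinuation visit in that period would include chemistry, but only for participants who stop.

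**Step 6. How many participants?** The documents give no rate of CPK above 2×ULN in this population, and none for its agreement between two visits. No count can be derived.

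**The case against.** **The triggers can be combined.** No passage says that its trigger is the only one. Each can be read as sufficient, so a site that follows the whole protocol would sample whenever either value is high. That reading is coherent and breaches nothing. However, it is stated nowhere. Section 8.2.5 sends sites to Appendix 2 for the tests and to Table 1 for their timing, and neither of those mentions the screening trigger.

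**Table A2-1 looks like a dropped word.** The sentence stands directly under a panel that includes CPK. This is plausible, but the table is the protocol's list of required safety tests, and as written it omits the repeat CPK.

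**The consequence is small.** This stands. CPK is measured in everyone at screening, baseline, Week 6, Week 12 and follow-up. Investigators may add tests or unscheduled visits. No eligibility criterion, stated stopping rule or efficacy endpoint depends on the Week 2 check, and all analyses are descriptive (Section 9.1).

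**A stronger reading, on adverse events of special interest.** Section 8.3.7 includes among these events "Creatine phosphokinase (CPK) values triggering a change in monitoring schedule and also when" any of three further conditions applies. A reader might infer that the disputed trigger therefore also alters 24-hour reporting and event counts. The documents do not support this, for two reasons.

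- Section 8.3.7 names neither 2×ULN nor Week 2 and does not define the change in monitoring. The confirmatory sampling above 10×ULN in A6-2.6 is another candidate.
- Both trigger values precede the first dose, because Section 4.1.2 puts Day 1 assessments before dosing. Section 8.3.1 records occurrences that begin before treatment as medical history and baseline conditions, apart from serious events caused by a protocol-mandated procedure. Section A3-5.2 starts special-interest reporting after treatment begins, and Section 9.4.5 summarises such events from the first dose onward.

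**Conclusion.** The protocol is inconsistent as written on the Week 2 CPK check. The trigger visit differs between A6-2.6 and the two tables, and Table A2-1 alone leaves out the repeat CPK. The inconsistency decides who has a safety sample, and whether it includes CPK, in a nominal 41-day period with no other routine CPK measurement.

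The point is minor. It concerns a conditional sample for a risk that the protocol rates as minimal, and it changes no efficacy result. It rests on the literal wording and on screening and baseline being separate samples, which the schedule and A6-2.6 both show. It does not extend to the reporting or counting of adverse events of special interest. The number of participants affected is unknown: it depends on how often CPK exceeds 2×ULN at one or both visits, which the documents do not report.

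**What to change.** Reconcile Table 1 footnote x, Table A2-1 and Section A6-2.6 so that all three name the same trigger visit or visits and the same Week 2 tests. The choice is a clinical decision for the sponsor, and this review does not recommend one. If more than one visit is meant to count, all three places should say so, and the test list should be checked against the four-sample comparison in A6-2.6. If the laboratory manual repeats the rule, it should carry the same wording.

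No change to Section 8.3.7 is needed on this account. The cost is amendment wording in three places, with no effect on sample size, analysis or visit structure.
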